The primary outcome is adherence to CV medications as measured by 12-month proportion of days covered (PDC). There are several complications in using this outcome, including a) a need to account for periods when subjects are not at risk of depleting their medication supply (see below for details), b) defining PDC when considering five medication classes (antihypertensives, statins, oral hypoglycemics, antiplatelets, and anticoagulants), c) accounting for number of other prescribed CV medications (more opportunities to miss days, and more opportunities to receive reminders), d) modeling the non-normal bounded distribution of PDC, and e) a desire to express results on a PDC difference (not risk ratio or odds ratio) scale. Analyses accounting for these complications are described below. Secondary outcomes include clinical events (e.g., event times for stroke, MI, mortality), utilization of care (e.g., hospitalizations or clinic visits for CV-related reasons), and costs of the interventions and of medical care. Given survival, subjects will be followed for at least 12 months following randomization to assess these secondary outcomes. Subjects who have more than one year of follow-up (up to 3 years depending on when they are enrolled during years 2-3) will continue to be followed for secondary outcomes.

Ascertainment of Outcomes

Data for the primary outcome PDC will be obtained using pharmacy records from each of the healthcare systems during the 365-day follow-up. To address complications a and b above: a) The assessment will be based on the number of outpatient days a patient has a medication available, among all days they were at risk of depleting that medication. At-risk days will be days during which a patient was prescribed the medication and should have depleted their supply, and will exclude days following death. Inpatient days will not be considered in the calculation. Note that at-risk days is medication specific, as medications may change during the one-year assessment period. b) We will consider three definitions of PDC: i) Medication-specific PDC: calculate PDC for each class of medication a patient is prescribed, ii) All-medication PDC: calculate PDC requiring all prescribed and at-risk medications be available on a day, and iii) Average PDC: calculate the average PDC across medications the patient is at risk of depleting on a day, and average over all days when at risk of depleting at least one medication.

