Study description: This individually randomized three-center trial will compare three behavioral nudges based on text and chatbot messaging with usual care to improve adherence to cardiovascular medications.

Setting: The study will be conducted in 17 primary care clinics within 3 health care systems (University of Colorado Health, VA Eastern Colorado Health Care System, and Denver Health Medical Center).

Design: The study will be an individually randomized controlled study with four treatment arms (details of interventions below). Patients become eligible for the study when identified through pharmacy refill data to have a 7-day gap in any prescribed CV medication refills. Eligible patients will be randomized to one of four arms. Randomization will be stratified within each of the clinics, and further stratified within clinics by patients with 1-2 vs 3 or more active CV medication classes at baseline, and using blocks of 4 patients to ensure balance within clinics over time. Thus, within each clinic and number of other medication stratum, each set of 4 consecutively enrolled subjects will be randomized to the four study arms. Treatments will be initiated immediately upon randomization, in response to the 7-day gap.

Intervention: The four treatment arms will be 1) usual care (control); 2) generic text message reminder; 3) text message behavioral nudges only; or 4) text message behavioral nudge plus a pre-programmed AI interactive chat bot designed to identify and resolve barriers to medication refill and adherence.

Delivery of treatments will be as follows:

For patients randomized to one of the three active intervention arms:

- If a patient gaps on a medication at baseline, they receive a text to refill that medication.
 - If a patient gaps on multiple medications at baseline, they receive only one text about all of the medications they gapped on.

- If a patient later gaps on any study medication, they will receive a reminder, regardless of whether they had gapped on or been prescribed the medication at baseline.
- If a patient is removed from a medication, no further texts are sent for that medication. Patients randomized to the control arm receive no texts or other reminders.

2. Study outcomes

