Treatment comparisons: Discussions with clinicians have indicated expressing results on a linear scale (PDC differences), as opposed to odds ratios or risk ratios, will be most appropriate for interpretation. This occurs naturally with the linear specification in 3.1.a and identity link in GEE. Estimation and inference will be carried out using the parameter estimates from the robust GEE estimation to construct expected PDC treatment differences. The estimand comparisons will be 12-month PDC, calculated by summing the 12 monthly longitudinal parameters, which incorporate the adjustments for early termination of some subjects using the weighted GEE approach. Primary hypotheses involve pairwise comparisons between each of the four study arms, and will be conducted using a multistage gatekeeper approach to account for the multiple treatment comparisons. In stage 1 of this approach, each of the three active intervention arms is compared with the control arm using significance level 0.05/3. In stage 2, if any of the three stage 1 tests is significant, the three pairwise comparisons among active intervention arms are tested with the Holm method using significance level (R/3)*(0.05/3), where R is the number of stage 1 tests that were significant (Dmetrienko et al., 2008).

3.1.b Defining composite PDC for multiple medications

There are 13 CV medication classes considered in this study, and the primary outcome is composite PDC across medications a patient is prescribed. There are several considerations in defining composite PDC, including which of a patient's medications to include in the composite PDC calculation, and calculation of composite PDC with differing lengths of follow-up for different medications.

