We will consider several alternate analyses for medication adherence.

Alternate definitions of PDC: Alternate definitions PDC2 and PDC3 and alternate composite PDC-C2 defined above will be analyzed using the same methods as for the primary definition PDC1-C1. These analyses will provide a better understanding of indirect effects of treatments, and of effects of treatments on all medications a patient is prescribed.

Sensitivity to inactive medications: Among medications gapping at baseline, we will repeat the primary analysis limiting our analyses to those medications that had at least one fill during the follow-up period. This will allow us to assess treatment effects among medications that are known to be active, removing medications that were cancelled but not indicated as such by the medical record.

Medication-specific adherence: We will calculate and analyze PDC for each medication individually, to allow analyses of heterogeneity of treatment effect (HTE) by drug class. Multiple comparisons will be adjusted for separately for each analysis using the gatekeeper approach described above.

Medication gaps: We will consider alternate ways of describing medication adherence behavior, including length of initial gap, time to subsequent gap, average length of gaps, and number of 7-day gaps.

3.1.e Secondary examinations of medication adherence

In secondary analyses we will examine several other questions related to medication adherence, including:

Predictors of medication gaps: We will examine predictors of patients having an initial gap of at least 7 days, using the initial pool of candidate patients, to identify types of patients or prescription characteristics for patients at highest risk for non-adherence. We will also examine predictors of subjects having a gap of at least 7 days while enrolled in the study.

Mechanism of treatment effects: We will carry out analyses examining mechanisms or mediators of treatment effect by considering direct responses to reminders, including time from first reminder to refill, and measures of patient engagement, e.g. number of patient text responses to reminders (intensive text and chatbot arms only).

Heterogeneity of treatment effect: We will carry out analyses examining HTE, specifically i) HTE between the three health care systems, and ii) HTE for patient characteristics or subgroups

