of particular interest. HTE analyses will be carried out using interactions as recommended in Kent et al., 2010 ²³ and will be considered exploratory.

3.1.f Original power analysis

We first estimate sample size required to achieve 80% power for the desired change in the primary outcome, then used current data to show we will be able to achieve this sample size.

Power and sample size: Required sample size was estimated for the primary outcome PDC during the 12 months following randomization. Preliminary data from the VA were used for these estimates. We made the following assumptions: a) Significance using two-sided level 0.05 tests, b) Power at least 80%; c) Difference between treatments in PDC of 10 percentage points; d) Bonferroni adjustment for the 6 pairwise comparisons among the 4 study arms, resulting in adjusted level 0.05/6 (a conservative alternative of the sequential gatekeeper approach to be used in the final analysis as described above, to simplify the calculation of power); e) Analysis stratified by health care system; and f) Within-system and within-treatment residual standard deviation of 12 month PDC equal to 0.22 (mean 0.732), obtained by analysis of 2,859 veterans during the period 01/01/2017 – 12/31/2017 who were prescribed the medications of interest in this study. The large SD is due to a highly left-skewed PDC distribution. (We base sample size estimation on t-tests rather than the proposed binomial models since we do not have estimates of quantities needed to carry out power simulations. We may be able to obtain data for the PDC outcome for a set of baseline patients, in which case we will consider a refined power analysis.) Using these assumptions and estimates, and comparing any two treatments using a linear model with the above residual standard deviation of PDC, we estimate using sample size functions in R that we will need N=119 subjects per treatment arm, total across the three health care systems, for a total of 476 subjects to be randomized across the three health care systems.

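### Effect heterogeneity by drug class is planned through separate gatekept analyses of each medication, with no adjustment across 13 classes and no arm-by-class interaction specified

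*Combined protocol and SAP*

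**What the plan says.** SAP 3.1.d, under Medication-specific adherence, states purpose and method together: "We will calculate and analyze PDC for each medication individually, to allow analyses of heterogeneity of treatment effect (HTE) by drug class". The only inferential rule attached is "Multiple comparisons will be adjusted for separately for each analysis using the gatekeeper approach described above".

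That gatekeeper is defined in SAP 3.1.a, under Treatment comparisons. In stage 1, "each of the three active intervention arms is compared with the control arm using significance level 0.05/3". If any of those tests is significant, the comparisons among active arms follow by Holm, "using significance level (R/3)*(0.05/3), where R is the number of stage 1 tests that were significant".

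On the number of classes, SAP 3.1.b says "There are 13 CV medication classes considered in this study". The protocol's Quantitative Analysis section uses a coarser grouping of five.

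SAP 3.1.e has its own paragraph on heterogeneity: "HTE analyses will be carried out using interactions as recommended in" a cited source, and the results are to be treated as exploratory. The factors it names are the three health care systems and patient characteristics or subgroups of particular interest. Drug class is not among them.

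**The concern.** There are two separate problems.

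First, the stated method does not answer the stated question. The gatekeeper compares arms within a class. Heterogeneity by class is a comparison of arm differences between classes. A significant result in one class beside a non-significant one in another reflects class size as well as effect, and is not evidence that the effects differ.

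Second, each class starts from a fresh 0.05. A chance finding in one of 13 classes would still carry a multiplicity-adjusted p-value, although the adjustment covers only the arms within that class.

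At stake are statements about which drugs' refills respond to the messages, which a health system could use to decide where to deploy them. The primary comparison of composite PDC is not at stake.

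**Working it through.** **Inputs**

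| Input | Value | Source |
|---|---|---|
| Stage 1 level | 0.05/3 per test, three tests | SAP 3.1.a |
| Unit of adjustment | each medication analysis separately | SAP 3.1.d |
| Number of classes | 13; or 5 groups | SAP 3.1.b; protocol, Quantitative Analysis |
| Allocation | equal ("each set of 4 consecutively enrolled subjects will be randomized to the four study arms") | SAP section 1, Design |
| SD of 12-month PDC | 0.22 | SAP 3.1.f |
| Design difference | 10 points | SAP 3.1.f |
| Patients enrolled | 1,235 + 7,266 + 1,000 = 9,501 | SAP, Achieved sample sizes |
| Class sizes, between-class correlation | not given; assumed | none |

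**1. The plan's own figure.** The documents state no error rate across classes. Their sample size does reproduce: difference 0.10, SD 0.22, two-sided level 0.05/6 and power 80% give 118.97 per arm by t-test, so 119, and 4 × 119 = 476.

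**2. Error within one class.** The nominal bound is 3 × 0.05/3 = 0.05. The three contrasts share one control arm. Integrating over the common control mean with critical value 2.394 gives 0.0445. Stage 2 opens only after a stage 1 rejection, so it adds nothing to the chance of any false claim when no arm has an effect.

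**3. Error across classes, no effect in any class.** For k independent classes the chance of at least one significant class is 1 − (1 − a)^k.

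- 13 classes, nominal: 1 − 0.95^13 = 0.487.
- 13 classes, shared control: 1 − (1 − 0.0445)^13 = 0.447.
- 5 groups, nominal: 1 − 0.95^5 = 0.226.
- 5 groups, shared control: 1 − (1 − 0.0445)^5 = 0.204.

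Patients can contribute to several classes, so the classes are correlated. The documents do not give the degree. A simulation of 200,000 trials with an assumed common correlation of arm means between classes gives:

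| Correlation | 13 classes | 5 groups |
|---|---|---|
| 0.2 | 0.42 | 0.20 |
| 0.5 | 0.32 | 0.17 |
| 0.7 | 0.24 | 0.14 |

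**4. Split verdicts under an equal effect.** Take one active arm against control in two classes, treated as independent, with assumed sizes of 600 and 100 per arm. The standardised difference is z = d / (SD × √(2/n)), and power p is the chance that the test statistic exceeds 2.394 in absolute value. The chance that exactly one class is significant is p₁(1 − p₂) + p₂(1 − p₁).

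| True effect in both classes | Power, n = 600 | Power, n = 100 | Verdicts differ |
|---|---|---|---|
| 3 points | 0.49 | 0.08 | 0.49 |
| 5 points | 0.94 | 0.22 | 0.75 |
| 10 points | 1.00 | 0.79 | 0.21 |

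These results depend strongly on the inputs. With 600 and 300 per arm at 10 points, the verdicts differ in under 1% of trials. With an assumed SD of 0.30 and 5 points (600 and 100 per arm), power is 0.69 and 0.11 and the verdicts differ in 65%.

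**5. What adjustment across classes would do.** A split over 13 classes gives 0.05/13 = 0.00385 per class and 0.00385/3 = 0.00128 per stage 1 test. The chance of any false class claim is then at most 1 − (1 − 0.00385)^13 = 0.049. A joint interaction test is instead a single test with (4 − 1) × (13 − 1) = 36 degrees of freedom.

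**The case against.** The best defence is that 3.1.d says only that the separate analyses allow heterogeneity to be studied, and that 3.1.e then says, in a sentence that is not itself limited to particular factors, that heterogeneity analyses use interactions and are exploratory. On that reading drug class is already covered. A reader might go further than the text and infer that heterogeneity by class is never tested; the documents do not support that. They do show that no arm-by-class interaction is specified. The list in 3.1.e omits class, and 3.1.d gives class a different rule. Class is also a medication-level factor on which one patient can contribute several observations, so a patient-level interaction does not carry over without a stated model.

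It can also be said that controlling the arm comparisons within each alternate analysis is a common choice, and that nothing in the SAP calls class results confirmatory. Both are true. This limits the consequence, but it does not make separate within-class tests a test of heterogeneity.

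Finally, the split-verdict figures rest on class sizes that the documents do not give. That stands, which is why they are shown as a range.

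**Conclusion.** The concern holds as a fault in an alternate analysis. Followed literally, 3.1.d gives each of 13 classes its own 0.05 and compares arms only within a class, and it is not reconciled with 3.1.e. The chance of at least one gatekept false class result is substantial: 0.45 for 13 independent classes, about 0.24 to 0.42 at assumed correlations of 0.7 to 0.2, and about 0.14 to 0.23 with five groups. That is roughly 3 to 10 times 0.05.

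A reader might infer that a false class claim is more likely than not. The figures do not show that: every scenario lies below one half, and all assume no effect in any class. Nor do the documents show that equal effects would be reported as different. Split verdicts under an equal effect range from under 1% to 75% in the cases computed, depending on the assumed effect, SD and class sizes. The type I error of the primary composite PDC comparison is unaffected.

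**What to change.** Replace the gatekeeper sentence in 3.1.d with a statement that heterogeneity by drug class follows the 3.1.e rule, and add drug class to the list there. Then specify:

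- a patient-by-medication model clustered on patient, with arm-by-class terms and a joint arm-by-class interaction test;
- which medications enter the model, since 3.1.d does not say;
- how the month terms are handled. The primary estimand sums 12 monthly parameters with arm-by-month terms, so the class model should either use 12-month PDC per medication or state another simplification, and should define the observation weights at medication level;
- pooling of sparse classes, fixed before unblinding;
- class-specific differences with confidence intervals, labelled exploratory. If p-values for class claims are kept, adjust them across classes.

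The cost is SAP wording and one extra model. The interaction test will have limited power (up to 36 degrees of freedom before pooling), so a non-significant result would not show that effects are equal. No class-specific result could be called confirmatory.

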3.2 Analysis of secondary outcomes

The secondary outcomes of clinical events, care utilization and cost will be analyzed using similar approaches as for the primary outcome but based on appropriate models, e.g. Cox survival models for time to clinical event or rehospitalization, generalized gamma regression for cost, etc. Standardization methods allow results to be expressed on interpretable scales such

as risk difference (e.g. Sjolander, 2016).²² Data will be analyzed using SAS (SAS Institute Inc., Cary, NC) and R software. In the table below, we provide an estimate of the secondary outcomes of interest based on a cohort of patients who would have been potentially eligible for the study from 2 of our health systems. This illustrates that we are able to capture these outcomes.

Outcomes of interest for the pragmatic trial. This is based on the cohort of patients identified from 2017-2018 who would have been eligible for the study and we followed them over time to assess outcomes						
Outcome	Patient population based on the	Outcomes of	Outcomes of			
	presence of specific comorbidity for	interest (DH)	interest (VA)			
	which the outcome is relevant	,	, ,			
Systolic BP - Mean (SD) mm Hg	All	131.2 (17.9)	133.8 (18.6)			
Diastolic BP - Mean (SD) mm Hg	All	78.7 (10.8)	79.4 (10.3)			
LDL - Mean (SD)	All	85.5 (38.6)	90.1 (33.1)			
Hemoglobin A1c - Mean (SD)	All	7.8 (1.9)	7.0 (1.6)			
All Cause Hospitalization (1 Yr.)	All	8.7% (792/9149)	13.6% (332/2447)			
Cause Specific Hospitalization		% (number of	% (number of			
		patients with	patients with			
		events/number of	events/number of			
		eligible patients for	eligible patients for			
		the outcome)	that outcomes)			
Hypertension Emergency	Hypertension	0.2% (14/7364)	0.4% (8/1877)			
Myocardial infarction (MI)	HTN/Hyperlipidemia/Diab/CAD	0.2% (22/9119)	0.3% (7/2402)			
Stroke	HTN/Hyperlipidemia/Diab/CAD/AF	0.1% (12/9149)	0.2% (4/2447)			
Heart Failure	HTN/CAD/AF	0. 8% (58/7546)	1.1% (23/2052)			
Hyperglycemia	Diabetes	0.1% (5/5122)	0.1% (1/1048)			
Atrial fibrillation (AF)	AF	2.3% (8/352)	2.9% (9/311)			
All Cause ED Visit (1 Yr)	All	1.9% (1700/9149)	4.5% (1093/2447)			
Cause Specific ED Visit						
Hypertension Emergency	Hypertension	0 (1/7364)	0.2% (3/1877)			
MI	HTN/Hyperlipidemia/Diab/CAD	0 (0/9119)	0.1% (3/2402)			
Stroke	HTN/Hyperlipidemia/Diab/CAD/AF	0 (0/9149)	0.1% (2/2447)			
Heart Failure	HTN/CAD/AF	0 (3/7546)	1.2% (25/2052)			
Hyperglycemia	Diabetes	0.9% (48/5122)	2.1% (22/1048)			
